13.3. Protocol Deviation Process

Investigators must report protocol deviations to the Sponsor within 10 working days of investigational site knowledge of the deviation by entering data into the protocol deviation log. Any protocol deviations that affect the rights, safety or well-being of the subject or the scientific integrity of the clinical investigation, including those which occur under emergency circumstances must be reported within 24 hours to the Sponsor and IRB if required by the IRB.

13.4. Corrective/Preventative Action

The Sponsor reserves the right to terminate an investigational site from the study for any of the following reasons:

- Repeated failure to complete Electronic Case Report Forms (eCRFs);
- Failure to obtain Informed Consent;
- Failure to report Serious Adverse Events within 24 hours of knowledge;
- Loss of or unaccountable investigational device inventory;
- Repeated protocol violations;
- Failure to enroll an adequate number of subjects

13.5. Data Quality Assurance

The following data quality steps will be implemented:

- All subject data relating to the investigation will be recorded on eCRFs unless directly transmitted to the Sponsor or designee electronically (e.g., laboratory data). The Investigator is responsible for verifying that data entries are accurate and correct by electronically signing the eCRF.
- The Investigator must maintain accurate documentation (source data) that supports the information entered in the eCRF.
- The Investigator must permit investigation-related monitoring, audits, and regulatory agency inspections and provide direct access to source data documents.
- The Sponsor or designee is responsible for the data management of this investigation including quality checking of the data. Predefined, agreed risks, monitoring thresholds, quality tolerance thresholds, controls, and mitigation plans will be documented.
- An Investigation Monitor will perform ongoing source data verification to confirm that data entered into the eCRF by authorized site personnel are accurate, complete, and verifiable from source documents; that the safety and rights of subjects are being protected; and that the investigation is being conducted in accordance with the currently approved CIP and any other investigation agreements, ISO GCP, and all applicable regulatory requirements.
- Records and documents, including signed ICFs, pertaining to the conduct of this investigation must be retained by the Investigator in the investigation site archive for at least 5 years after the end of the investigation unless local regulations or institutional policies require a longer retention period. No records may be destroyed during the retention period without the written approval of the Sponsor. No records may be transferred to another location or party without written notification to the Sponsor.

14. TERMINATION OF STUDY OR STUDY SITE PARTICIPATION

The Sponsor may terminate the study at any time. Reasons for study termination may include but are not limited to any of the following:

- Adverse events unknown to date (i.e., not previously reported in any similar investigation or in market use with respect to their nature, severity, and/or duration).
- Increased frequency, severity, and/or duration of known, anticipated, or previously reported AEs.
- Medical or ethical reasons affecting the continued performance of the investigation.
- Difficulties in the recruitment of subjects.
- Cancellation of device development.

If the study is terminated prior to the completion of expected enrollment for any reason, all participating centers will be notified within five working days. All subjects already enrolled will

continue to be followed for the planned course of study described in this protocol. The study will be terminated following the final follow-up visit of the last enrolled subject.

In addition to the corrective actions listed in **Section 13.4**, the Sponsor reserves the right to terminate study site participation and remove appropriate study materials at any time. Specific instances that may precipitate such termination include but are not limited to the following:

- Failure to meet minimum subject enrollment requirements
- Failure to comply with protocol specified procedures and documentation
- Failure to comply with Good Clinical Practice

The site Investigator may also discontinue study participation with suitable written notice to the Sponsor.

15. ETHICS/PROTECTION OF HUMAN SUBJECTS

15.1. Statements of Compliance

This clinical investigation shall be conducted in accordance with the ethical principles that have their origin in the Declaration of Helsinki, and 21 CFR Part 812, 50, 54, 56. The clinical investigation shall not begin until the required approval from the IRB has been obtained, if appropriate. Any additional requirements imposed by the IRB, or regulatory authority shall be followed.

15.2. Institutional Review Board (IRB)

Each participating institution must provide for the review and approval of this protocol and the associated informed consent documents and recruitment material by an appropriate IRB. Any major amendments to the protocol or consent materials must also be approved before they are placed into use.

15.3. Informed Consent Process

Informed consent is a process that is initiated prior to the individual's agreeing to participate in the study and continues throughout an individual's study participation. Discussion of risks and possible benefits of this therapy will be provided to the subjects and their families. Consent forms describing in detail the study interventions/products, study procedures, and risks are given to the subject and written documentation of informed consent is required prior to starting intervention/ administering study product.

Consent may be provided by 1) individual subject providing informed consent; 2) assent of a guardian, healthcare proxy, or welfare attorney on behalf of a subject without capacity to consent (vulnerable or incapacitated individual). Details of the process for obtaining and documenting informed consent are provided in Appendix 3. Failure to obtain informed consent prior to initiation of study treatments will need to be documented as a protocol deviation and be reported in accordance with regulations.

15.4. Subject Confidentiality

Confidentiality of data shall be observed by all parties involved at all times throughout the clinical investigation. All data shall be secured against unauthorized access.

The privacy of each subject and confidentiality of his/her information shall be preserved in reports and when publishing any data. The Principal Investigator or institution shall provide direct access to

source data during and after the clinical investigation for monitoring, audits, IRB review and regulatory authority inspections. As required, the Principal Investigator or institution shall obtain permission for direct access to source documents from the subject, hospital administration and national regulatory authorities before starting the clinical investigation.

16. PROTOCOL AMENDMENTS

The Protocol, CRFs, ICF and other subject information, or other clinical investigation documents shall be amended as needed throughout the clinical investigation, and a justification statement shall be included with each amended section of the document. Proposed amendments to the Protocol shall be agreed upon between the Sponsor and Principal Investigator(s), or the coordinating investigator. The amendments to the Protocol and the subject's informed consent form shall be notified to, or approved by, the IRB and regulatory authorities as required. For non-substantial changes (e.g., minor logistical or administrative changes, change of monitor(s), telephone numbers, renewal of insurance) not affecting the rights, safety and well-being of human subjects or not related to the clinical investigation objectives or endpoints, a simple notification to the IRB and, where appropriate, regulatory authorities can be sufficient. The version number and date of amendments shall be documented.

17. PUBLICATION POLICY

CytoSorbents manages its clinical studies in an ethical and rigorously scientific manner, working with leading experts in the field, to clearly and publicly demonstrate the benefits, risks, and value of the DrugSorb™-ATR Device to caregivers and study subjects alike. We accept the obligation to facilitate publication of medically important clinical data in a timely, objective, accurate, and balanced manner, regardless of the outcome of this trial. To ensure that an accurate record of the study data is presented to the public, CytoSorbents understands the need to allow sufficient time for careful preparation, analysis, interpretation, and review of study data and reports prior to their dissemination.

Safety and Efficacy Data generated for all prespecified primary and secondary endpoints, shall be compiled, analyzed, reviewed, and published in the following manner:

- The Principal Investigator(s) and Sponsor shall compile and disseminate a clinical summary report that shall be disseminated to CytoSorbents (as Sponsor), all participating local and central IRBs, and the FDA. Data from this Summary Report shall also be published on the ClinicalTrials.Gov website simultaneously.
- Following database closure, a study publication shall be submitted to a peer reviewed journal within 18 months of database closure. In the event that the study is terminated early, a publication of this data will be submitted within 12 months of database closure.

20. APPENDICES

Appendix 1: Adverse Event Reporting

An adverse event (AE) is any untoward medical occurrence (signs, symptoms, abnormal laboratory findings) in a subject regardless of relationship to the device or procedure. Throughout the study, the Investigator or designee will determine adverse event (AE) occurrences. All AEs that occur starting from subject enrollment through follow-up will be reported. As a matter of semantics, AEs that are new onset or worsen in severity *after the start of the cardiopulmonary bypass procedure* are considered Treatment-emergent AEs. This term does *not* include adverse events occurring *prior* to the start of CPB but *after* the signing of the ICF (assent or consent). As previously discussed in **Section 11.6**, only the treatment-emergent AEs will be included in the safety analysis. This will be further detailed in the SAP.

Each adverse event is considered to be either anticipated or unanticipated as described below. The site is required to report the classes of adverse events that occur in the study (AE, SAE, and UADE) as described further below.

Severity Assessment

The Investigator will assess each adverse event for severity in accordance with the following categories: mild, moderate, severe, life-threatening, or death.

The severity assessment is distinct from the seriousness assessment (see definition of SAE below).

Serious Adverse Events

A serious AE (SAE) is defined as any untoward medical occurrence that meets one or more of the following criteria:

- led to death;
- led to a life-threatening illness or injury;
- led to in-patient hospitalization or prolongation of existing hospitalization;
- led to disability or permanent damage to a body structure or body function;
- led to fetal distress, fetal death, congenital anomaly or birth defect;
- required medical or surgical intervention to prevent permanent impairment or damage; or
- Important medical events that may not result in death, be life-threatening, or require hospitalization may be considered SAEs when, based upon appropriate medical judgment, they may jeopardize the subject and may require medical or surgical intervention to prevent one of the outcomes listed in this definition.

Definition of Hospitalization

Adverse events requiring hospitalization or extended hospitalization should be considered serious. In general, hospitalization signifies that the subject has been detained (usually involving an overnight stay) at the hospital or emergency ward for observation and/or treatment. When in doubt as to whether hospitalization occurred or was necessary, the AE should be considered as serious. *Planned hospitalization for pre-existing condition, or a procedure required by the Clinical Investigation Plan, without a serious deterioration in health is not considered a serious adverse event.*

Serious AEs occurring after 30 days post-operation are to be reported to the Sponsor if, in the judgment of the Investigator, there is an association between the event and the previous use of the device under investigation.

Causality Assessment

The Investigator will assess each adverse event for relationship to the following (causality), and relationship classified as unrelated, unlikely related, possibly related, probably related, or definitely related:

Investigational Treatment/Device: An investigational device/treatment-related adverse event is one which in the judgment of the Investigator, results as a consequence of the investigational device/treatment. Clinical judgement in conjunction with the relevant documents, such as the Investigator's Brochure and the Clinical Investigational Plan shall be applied in the determination of whether the AE might be related to the device/treatment. The presence of confounding factors, such as concomitant medication/treatment, the natural history of the underlying disease, other concurrent illness or risk factors shall be considered.

Surgical Procedure: The investigator will distinguish between the events potentially related to CPB and the investigational device from those related to the underlying surgical procedures. A procedure-related adverse event is one which, in the judgment of the Investigator, results as a consequence of the subject's surgical procedure and is not specific to the investigational device/treatment used or the associated CPB circuit. Complications occurring during a procedure are considered not related to the device if the complication would have been applied to the subjects in the absence of the investigational device use/application. Adverse events that have previously been determined to be related to the investigational device should not also be assessed as being related to the surgical procedure.

Causality assessment will also be performed during CEC adjudication of relevant events. Guidelines for CEC causality assessments are provided in the CEC charter.

Action Taken for Adverse Events

The Investigator or designee will record the action taken for the AE within the electronic Case Report Form (eCRF) in accordance with the following categories: treatment interrupted, treatment withdrawn, medication, procedure/intervention, transfusion, other/unknown, or none.

Outcome

The Investigator or designee will record the outcome of the AE within the electronic Case Report Form (eCRF) in accordance with the following categories: resolved without sequelae, resolved with sequelae, ongoing, or resulted in mortality.

Follow-up of Adverse Events

Every reasonable effort will be made to follow up with subjects who have AEs. Any subject who has an ongoing AE that is related to the investigational medical device at the 30-day Follow-up Evaluation will be followed up, where possible, until resolution or stabilization. This will be completed at the Investigator's (or designee's) discretion. Any subject who has an ongoing AE that is not related to the investigational medical device at the 30-day Follow-up Evaluation can be closed out as ongoing at the Investigator's discretion.

Adverse Device Effect:

An adverse device effect (ADE) is an AE related to the use of an investigational medical device. This definition includes AEs resulting from insufficient or inadequate instructions for use, deployment,

installation, or operation, or any malfunction of the investigational medical device. The definition also includes any event resulting from use error or from intentional misuse of the investigational medical device. These events can be classified as either serious or not serious in accordance with the definition for SAEs above. Serious adverse device effects are also commonly referred to by the abbreviation SADE.

Unanticipated Adverse Device Effect:

An unanticipated adverse device effect (UADE) is any adverse device effect which by its nature, incidence, severity or outcome has not been identified in the current version of the risk analysis report. These events can be classified as either serious or not serious in accordance with the definition for SAEs above. In the event of a possible UADE, the subject blind may be broken as per **Section 6.3.3** above. This will enable confirmation of relationship between the adverse event and device exposure and facilitate appropriate safety procedures as well as regulatory reporting per guidelines.

Anticipated Adverse Events/Device Related Adverse Events

A variety of complications are expected to occur in subjects undergoing CPB and cardiothoracic surgery, regardless of whether or not DrugSorb™-ATR is used. These may include, but are not limited to:

Serious, but less common, risks:

- Bleeding during or after the surgery including bleeding in relation to anticoagulation
- Blood clots that can cause heart attack, stroke, or lung problems
- Heparin-induced thrombocytopenia
- Bypass induced thrombocytopenia
- Reduction in platelets
- Infection, including pneumonia
- Organ injury including:
 - Respiratory damage causing breathing problems or failure to wean from the ventilator
 - Cardiac dysrhythmias/arrhythmias
 - Kidney injury or renal failure
 - Cognitive impairment
- Death

Less serious, but more common risks and adverse events:

- Low-blood pressure
- Nausea and/or vomiting
- Hypothermia and/or Chills
- Allergic response to device materials
- Reduction in platelet count
- Reduction in white blood cell count
- Reduction in proteins (albumin, total protein)
- Coagulation within device
- Heparin-induced thrombocytopenia

Potential Adverse Device Events Directly Related to DrugSorb™-ATR:

- Removal of drugs and hormones
- Allergic response to device materials
- Reduction in platelet count
- Reduction in white blood cell count
- Reduction in proteins (albumin, total protein) which may increase with CPB duration.
- Reductions in serum calcium (as a consequence of reductions in albumin)
- Coagulation within device
- Infection
- Blood loss
- Hemolysis
- Device leakage
- Circuit leakage
- Death

Investigator Reporting:

The Investigator at each participating center is ultimately responsible for reporting adverse events to the Sponsor or its designee. The information to be reported on the adverse event should include the start date of the adverse event, treatment, resolution, and assessment of both the seriousness and the relationship to the investigational device. The Investigator (or designee) is required to complete the adverse event eCRF at each study visit if an adverse event occurs. One adverse event eCRF must be completed for each adverse event. The timing of mandatory Investigator reports is provided in **Table 4**.

If there is a device malfunction or other observation, the Device Observation CRF requires the Investigator to indicate if the observation resulted in an adverse event and indicate if complications are related to the device, procedure or underlying disease.

Sponsor Reporting:

Reports will be provided to the FDA as required under §812.150. The details will be provided in the Study Reference Manual for the trial.

Appendix 2: Clinical Laboratory Evaluations

Clinical chemistry:	Hematology:
Alanine aminotransferase ^a Albumin Alkaline phosphatase ^a Aspartate aminotransferase ^a Blood urea nitrogen Calcium Ionized Calcium ^a Chloride Creatinine Direct bilirubin ^a Gamma-glutamyl transferase ^a Glucose Potassium Sodium Total bilirubin ^a Total protein	Hematocrit Hemoglobin Platelet count Red blood cell count White blood cell (WBC) count Differential ^a
Coagulation tests:	Other, including cardiac biomarkers
Coagulation Panel: Activated partial thromboplastin time International normalized ratio Prothrombin time Fibrinogen ^a Point of Care Test(s): Activated clotting time (ACT) [refer to Schedule of Assessments for specific timing of sampling]	Serum pregnancy test ^b Cardiac troponin (cTn) ^c

^a Performed only if part of routine standard of care. Sponsor agrees to forego the data if the assessments are not performed and recorded^b Performed in serum at Screening for all females of child-bearing potential. Pre-consent test results done during the current admission MAY be used. Pre-consent test results done before the current admission MAY NOT be used.^c Performed in serum Screening for all subjects. Post-op testing will be per institutional standard of care, or as indicated by symptoms and concern for perioperative myocardial infarction

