The UDPB scale is a standardized bleeding definition that was specifically designed by experts to capture early bleeding after cardiac surgery and is based on the following 9 criteria occurring either in surgery or during the first postoperative day: (1) delayed sternal closure, (2) postoperative chest tube output, (3) packed red blood cell transfusion, (4) fresh frozen plasma transfusion, (5) platelet transfusion, (6) cryoprecipitate transfusion, (7) use of factor concentrates, (8) use of recombinant activated factor VII (rFVIIa), and (9) surgical re-exploration. [17] The UDPB scale defines 5 perioperative bleeding classes (0-4) as shown in **Table 1** (below). Importantly, it has been demonstrated that higher classification within the UDPB (starting from moderate, up through severe-massive) is correlated with higher 30-day mortality rate, thus making the standardized definition both a useful descriptive tool as well as a predictor of clinical outcome. [17]

Table 1. Bleeding Class According to the Universal Definition of Perioperative Bleeding in Adult Cardiac Surgery

Class	Sternal Closure delayed	Postoperative chest tube blood loss within 12 h (mL)	PRBC (units)	FFP (units)	PLT (units)	Cryoppt	PCCs	rFVIIa	Reexploration/tamponade
0	No	< 600	0*	0	0	No	No	No	No
1	No	601-800	1	0	0	No	No	No	No
2	No	801-1000	2-4	2-4	Yes	Yes	Yes	No	No
3	Yes	1001-2000	5-10	5-10	N/A	N/A	N/A	No	Yes
4	N/A	>2000	>10	>10	N/A	N/A	N/A	Yes	N/A

Class 0 = Insignificant; Class 1 = Mild; Class 2 = Moderate; Class 3 = Severe; Class 4 = Massive

PRBC = packed red blood cells; FFP = fresh frozen plasma; PLT = platelet concentrates; Cryoppt = Cryoprecipitate; PCCs = prothrombin complex concentrates = rFVIIa, recombinant activated factor VII; N/A, not applicable

For purposes of UDPB, PRBC, PLT, FFP, and Cryoppt transfusions are counted beginning **at chest closure**. PCC and rFVIIa transfusions are counted beginning at the start of the procedure.

* Correction of preoperative anemia or hemodilution only; the number of PRBCs used should only be considered in the UDPB when accompanied by other signs of Perioperative bleeding. Prophylactic/preoperative transfusion of blood products and factor concentrates do not contribute to UDPB.

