11. STATISTICAL CONSIDERATIONS

General statistical considerations: descriptive summaries will be presented using mean with standard deviation (SD), median, minimum and maximum for continuous variables and as count and percent of subjects for categorical variables. Inferential statistical tests will be two-sided, and use an alpha (α) critical value of 0.05, unless noted otherwise. Statistical analysis will be carried out using SAS Version 9.4 or later and/or R software language.

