11.1. Statistical Power and Sample Size Determination

Up to 140 subjects meeting the study inclusion criteria (**Section 4.4.1**) will be randomized in a 1:1 ratio to the treatment and control arms. As noted above (**Section 6.2**), in order to maintain the balance between sites in terms of numbers of subjects randomized, study sites will be capped at randomizing a maximum of 15% of the overall study sample. Allowing for 5% dropouts, at total of 114 subjects (57 per arm) are expected to be evaluable for effectiveness and safety. Sample size is based on assumed effect size for the primary effectiveness Win Ratio sub-components (**Table 3**), and can be calculated via an iterative simulation process with programming code available in an appendix to Redfors et al. (2019).[11] With a Finkelstein – Schoenfeld test, a total of 57 subjects per arm ensures power of $\geq 99.7\%$ for the primary effectiveness endpoint at the final analysis, using a two-sided alpha (α) of 0.05. [10] With this same per arm sample size, power for the key secondary endpoint is estimated at $>99.9\%$ assuming a $40\% \pm 40\%$ mean difference between treatment and control, based on a two-

sample t-test assuming equal variance and a two-sided alpha of 0.05. For the 24-hour CTD secondary endpoint, assuming a treatment arm volume of 480 ± 253 mL and control arm volume of 800 ± 253 mL [8] [a discount is applied (see **Table 3** for details) to bring the Active arm up to ~40% reduction on the Control arm], power is similarly estimated at >99.9%. Power for comparisons of platelet transfusions between the treatment arm (0.32 ± 0.9 units) and control arm (1.6 ± 2.2 units) [13] is estimated at 98.0%, based on a two-sample t-test assuming unequal variance and a two-sided alpha of 0.05. Similarly, power for PRBC transfusions between the treatment arm (1.3 ± 2.1 units) and control arm (4.4 ± 5.7) [13] is estimated at 96.7%.

Overall study sample size is designed to provide adequate power for the primary effectiveness endpoint, the key secondary endpoint, and succeeding three secondary endpoints. Sample size and power for all secondary endpoints were calculated using PASS 2021 (NCSS, LLC. Kaysville, UT, USA, ncss.com/software/pass).

The null hypothesis for the primary composite endpoint is represented by:

H_0 : The distributions of the components are the same in the two treatment groups.

The alternative hypothesis for the primary composite endpoint is represented by:

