^e Baseline EKG is required on file within the subject's medical record pre-op but does not need to have been performed within the 2 days prior to the day of surgery. Post-op EKG is only mandated in the event of possible MI

^f In all females of child-bearing potential. Performed in serum. Pre-consent test results done during the current admission MAY be used. Pre-consent test results done before the current admission MAY NOT be used.

^g Refer to Appendix 2 for a list of evaluations in the hematology, clinical chemistry, cardiac biomarker, and coagulation tests. During Screening, if consented subjects enter the Operation Phase without post-consent evaluation of hematology, clinical chemistry, or coagulation tests to record, the last pre-consent laboratory values MAY be used. Post-op cTn is only mandated in the event of possible MI

^h Vital signs include supine blood pressure, pulse rate, respiratory rate, oxygen saturation, and body temperature.

ⁱ Duration of CPB = time from the start of CPB to end of CPB, which may differ from duration of operation. Flow rate and flow duration for the device will be recorded q30±5min while patient is on CPB; flow rates are not mandated while subject is on hypothermic circulatory arrest (HCA).

^j Details regarding the surgical type will be recorded. Delayed sternal closure will be recorded. *Re-exploration/re-thoracotomy will be recorded according to the same schedule as AEs and documented in the re-operation eCRF.*

^k ACT will be obtained once at 30min into CPB ±15min, and once within 30min post-protamine administration (post-CPB). Intraoperative ACT is documented in the ACT log, and not recorded in the

Coagulation Test eCRF.

- ¹ During the operation phase, arterial blood gas analysis will be obtained at the following time periods: within 30min pre-CPB, 30 ± 15min into CPB, within 30min post-CPB, and upon admission to the ICU
- ^m Blood product administration will be monitored and recorded from the point of consent through discharge. Cell Saver will **not** be included as blood product administration. Blood loss and bleeding events will be monitored and recorded through follow-up, and drainage will be monitored from chest closure to 12h post-op (for UDPB class) and continued from 12hr post-op through at least 24h post-operation.
- Measurement of drainage after 24h and through time of chest/mediastinal drain removal will be per SOC.

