### 3.6 Homogeneity Across Subgroups of Interest

The following analysis will be carried out on the mITT, PP, i-CABG mITT, and i-CABG PP populations with no imputation for missing data.

Appropriate descriptive statistics of the primary effectiveness endpoint and its components will be presented by treatment group (treatment vs control) within the subgroup categories below. The purpose of this analysis is not to assess significance of the treatment effect (treatment vs. control on the primary effectiveness endpoint and its components) within subgroups but to assess consistency of treatment effect on the primary effectiveness endpoint and its components across subgroups.

The following is a list of the subgroups to be investigated. For each subgrouping, in order to assess homogeneity of treatment effect on the primary effectiveness endpoint and its components, assessment of treatment-by-subgroup category interaction will be carried out in a similar manner as discussed previously for assessing homogeneity across regions.

We will evaluate the consistency of effectiveness on the primary effectiveness endpoint and its components (homogeneity), in the following subgroups:

1. Sex: Male vs Female
2. Age: <65 vs.  $\geq 65$
3. CABG vs. other procedures
4. Pre-existing clinical risk factors
  - a. EuroScore II <7%;  $\geq 7\%$ )
  - b. STS mortality risk score (<4% [low], 4%-8% [intermediate], >8% [high])
  - c. Baseline thrombocytopenia (platelet count <150,000  $\mu\text{L}$  vs.  $\geq 150,000 \mu\text{L}$ )

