#### **5.4.1.2 Other Continuous Secondary Effectiveness Endpoints**

Total platelet/PRBC transfusions in volumes from end of operation through the duration of the index hospitalization (initial discharge from the hospital) will be analyzed based on the observed data using two-sample t test. The p-value and estimated mean difference along with the 95% CI will be provided between the treatment and control group.

Wilcoxon rank sum test based on the observed data in volumes will be performed if the normality assumption is invalid. The nonparametric p-value will be provided as well as median treatment difference in volumes for total platelet/PRBC transfusions.

The same analyses using transfusion data measured in units will be conducted as the supplemental analyses.

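### The two alpha-controlled transfusion tests omit surgery type and the baseline blood counts already collected: valid, but less precise than they could be

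*Protocol*

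**What the plan says.** **Tests.** SAP 5.4.1 makes ANCOVA on treatment group and type of surgery (where judged suitable) the default for continuous secondary endpoints, and 5.4.1.1 applies it to 24-hour chest tube drainage. SAP 5.4.1.2 makes an exception for platelet and PRBC volumes, which "will be analyzed based on the observed data using two-sample t test"; a Wilcoxon rank sum test replaces it if normality fails. The protocol synopsis and section 11.3 also give two-sample t-tests with a Mann-Whitney fallback. No reason is given for leaving the ANCOVA default.

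**Role.** SAP 3.7 and 5.1 place platelet and PRBC transfusions fourth and fifth in the fixed testing sequence. UDPB class, re-exploration and fatal bleeding follow.

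**Available covariates.** Protocol Appendix 2 lists "Hematocrit Hemoglobin Platelet count Red blood cell count"; in the hematology panel only the differential carries the footnote for tests done solely as standard of care. Table 6 schedules hematology at Screening, and its footnote g adds that "the last pre-consent laboratory values MAY be used" when no post-consent result exists. Protocol section 9 treats a missed required assessment as a deviation. SAP 3.4 defines baseline as the last value before the index operation. Planned surgery type is a randomisation stratum (protocol 6.1).

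**Planned use.** For effectiveness, the SAP uses baseline platelet count only as a subgroup split, "Baseline thrombocytopenia (platelet count <150,000" against higher counts (3.6). It plans no effectiveness use of baseline hemoglobin.

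**The concern.** A subject who enters surgery anemic or with a low platelet count may plausibly be transfused more in either arm. The documents lean that way. SAP 3.6 lists thrombocytopenia among pre-existing clinical risk factors. The UDPB table in protocol section 3 carries a footnote, "Correction of preoperative anemia or hemodilution only", that keeps such PRBCs out of the bleeding class. The PRBC endpoint has no similar exclusion, although it counts only from the end of the operation. Protocol 6.1 stratifies on surgery type because bleeding risk differs by procedure.

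If these variables are prognostic, the unadjusted tests leave explainable variation in the error term. The cost is wider intervals on two endpoints that gate the rest of the sequence, and lower power if the true effects fall short of plan.

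**Working it through.** **Inputs.** Alpha: "Inferential statistical tests will be two-sided, and use an alpha (α) critical value of 0.05, unless noted otherwise" (protocol 11). Platelets: "platelet transfusions between the treatment arm (0.32 ± 0.9 units) and control arm (1.6 ± 2.2 units" (protocol 11.1), a difference of 1.6 − 0.32 = 1.28. PRBC: "power for PRBC transfusions between the treatment arm (1.3 ± 2.1 units) and control arm (4.4 ± 5.7" (protocol 11.1), a difference of 4.4 − 1.3 = 3.1. Evaluable subjects: 57 per arm in the protocol, 65 per arm in the SAP. Stated power: 98.0% and 96.7%, assuming unequal variances.

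**Step 1: reproduce the stated power (57 per arm).** The Welch test has SE = √[(s₁² + s₂²)/n], noncentrality = difference/SE, and Satterthwaite degrees of freedom.
- Platelets: SE = √[(0.81 + 4.84)/57] = 0.315; noncentrality = 1.28/0.315 = 4.07; df = 74.2; power 97.99%.
- PRBC: SE = √[(4.41 + 32.49)/57] = 0.805; noncentrality = 3.1/0.805 = 3.85; df = 70.9; power 96.71%.

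Both stated figures reproduce. At 65 per arm the same inputs give 99.0% and 98.2%. The inputs are in units, whereas the synopsis and SAP attach the powers to volume in mL, so they are not strictly powers for the tested variable.

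**Step 2: effect of adjustment at the planned effects.** Let R² be the share of within-arm variance that the covariates explain. The documents give no value, so 0.05 to 0.30 is assumed. Both SDs are multiplied by √(1 − R²), and the interval narrows by 1 − √(1 − R²).

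| R² | Interval narrower by | Platelets, n=57 | PRBC, n=57 | Platelets, n=65 | PRBC, n=65 |
|---|---|---|---|---|---|
| 0 | 0 | 98.0% | 96.7% | 99.0% | 98.2% |
| 0.05 | 2.5% | 98.5% | 97.4% | 99.3% | 98.7% |
| 0.10 | 5.1% | 98.8% | 98.0% | 99.5% | 99.0% |
| 0.20 | 10.6% | 99.4% | 98.9% | 99.8% | 99.5% |
| 0.30 | 16.3% | 99.8% | 99.5% | 99.9% | 99.8% |

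At 57 per arm the largest gains are 1.8 points (platelets) and 2.8 points (PRBC).

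**Step 3: a smaller true effect.** The planned reductions are 1.28/1.6 = 80% and 3.1/4.4 = 70%. For UDPB and chest tube drainage, protocol Table 3 discounts to about 40%. Applying 40% to the transfusion means is an assumption made here, as is scaling the treatment-arm SD with its mean. At 65 per arm:
- Platelets: difference 0.64, SDs 1.32 and 2.2, SE = √[(1.74 + 4.84)/65] = 0.318.
- PRBC: difference 1.76, SDs 3.42 and 5.7, SE = √[(11.70 + 32.49)/65] = 0.824.

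| R² | Platelets | PRBC |
|---|---|---|
| 0 | 51.3% | 56.2% |
| 0.10 | 55.6% | 60.6% |
| 0.20 | 60.6% | 65.7% |
| 0.30 | 66.3% | 71.5% |

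The gain is about 4 to 15 points for both endpoints.

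**Step 4: skewed counts.** SDs larger than their means, as in both arms, make normality doubtful. PRBC was therefore simulated as overdispersed counts (65 per arm, control mean 4.4 and SD about 5.7, 40% reduction, 3,000 trials per setting). Power without and with adjustment for hemoglobin was:
- t-test against ANCOVA with robust errors: 56% and 57% at R² = 0.06, 58% and 62% at 0.13, 59% and 68% at 0.25.
- Wilcoxon against rank ANCOVA: 46% and 48%, 51% and 56%, 59% and 70%.

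Type I error stayed at 4.3-5.3%. No platelet simulation was run at the 40% reduction.

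**The case against.** The strongest reply is that nothing is wrong with the planned tests. Under 1:1 randomisation the t-test and Wilcoxon test are valid, and their standard errors already allow for chance imbalance in hemoglobin or platelet count. A reader might infer that imbalance biases the comparison. The documents do not support that, and this part of the objection stands in full.

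A reader might also infer that these endpoints are underpowered. At the protocol's own effects they are not, and a matched negative-binomial simulation at 57 per arm gave about 99% Welch power for both. The larger gains require a 40% reduction, which the documents assume for other endpoints and not for transfusion. This also stands.

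Nor do the documents show that the covariates are strongly prognostic. The UDPB footnote governs bleeding class, not this endpoint. The protocol attributes bleeding to ticagrelor-induced platelet dysfunction rather than low counts, and it excludes counts below 50,000. At R² = 0.06 the simulated t-test gain of one point is close to the Monte Carlo error of about 0.9 points per figure.

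The objection does not explain why the SAP leaves its own ANCOVA default for these two endpoints and drops a stratum chosen for its link to bleeding risk. Adjustment needs no new data, and the SAP has already replaced the protocol's t-test with ANCOVA for chest tube drainage.

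**Conclusion.** The point holds as a low-cost gain in precision on two alpha-controlled endpoints. It is not a finding of bias, invalidity or inadequate planned power.

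The expected benefit is an interval about 3-16% narrower if R² is 0.05-0.30. Power rises by no more than about 2-3 points at the planned effects with 57 per arm. It rises by about 4-15 points with 65 per arm and R² of 0.10-0.30 if the true reduction is nearer 40%.

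These sizes rest on an R² range that the documents do not supply and, for the last figure, on an assumed effect and treatment-arm SD. The case for platelet count is weaker than for hemoglobin, because its prognostic value is not shown. The interval figures apply to the linear model and do not carry over to the rank-based fallback.

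**What to change.** Before unblinding, revise SAP 5.4.1.2 as follows:
- Main test for each transfusion volume: a linear model with treatment, planned surgery type as stratified, and the SAP 3.4 baseline value of hemoglobin (for PRBC) or platelet count (for platelets), with heteroscedasticity-robust standard errors because the planned SDs differ between arms.
- Nonparametric fallback: rank ANCOVA on the same covariates.
- Supportive: the unadjusted t-test and Wilcoxon test.
- Endpoints and testing order: unchanged.

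Align the protocol synopsis and section 11.3, which specify the unadjusted tests; an SAP-only edit would leave the two documents in disagreement on alpha-controlled analyses.

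The cost is SAP and protocol wording and a few lines of code, with no new data and no extra subjects. If the covariates prove weakly prognostic, little is gained.
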